7.2.1 Selected Items from the Bladder Pain/Interstitial Cystitis Symptom Diary

The BPIC Symptom Diary⁵³ is a self-reported instrument designed to assess symptoms of bladder pain/interstitial cystitis on a daily basis. The adapted version that will be used in this study is comprised of 2 bladder pain NRSs (average and worst pain), and other urinary symptoms (2 items). The two items assess urinary urgency (In the past 24 hours, how often did you have to rush to get to the bathroom to urinate?) and the constant need to urinate (In the past 24 hours, did you have a constant need to urinate?).

This assessment will be administered to participants ≥ 12 years of age at baseline, then daily through Week 6, followed by weekly to Week 24.

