2.3.2 Secondary Efficacy Endpoints

The key secondary endpoint is the time to resolution of bladder pain as measured by ageappropriate COAs. Resolution of pain is defined as participants achieving a score on the relevant COA that does not exceed "mild pain," confirmed with 2 consecutive scores, without use of prescription pain medications (not PRN or "as needed") or the use of supportive bladder care, specifically continuous bladder irrigation and nephrostomy tubes.

Mild bladder pain is defined as:

- In participants ≥12 years of age: a score ≤3 on the worst daily pain question from the Bladder Pain/Interstitial Cystitis Symptom Diary (BPIC SD).
- In participants 3 to 11 years of age: a score ≤2 on the Wong-Baker FACES® Pain Rating Scale.

The analysis will include all participants whose pain scores exceed "mild pain" at randomization, or who are receiving prescription pain medications (not PRN or "as needed") or supportive bladder care at randomization. Use of prescription pain medications (not PRN or "as needed") or supportive bladder care will be considered equivalent to pain that exceeds "mild pain." If the pain scores at randomization are missing, the screening pain scores will be used. Otherwise, the participant will not be included in the analysis.

This endpoint will not be assessed in participants <3 years of age as there is no COA that has been validated for this purpose. Instead, data regarding pain behaviors will be collected in this age group using the Patient-Reported Outcomes Measurement Information System® (PROMIS) Parent Proxy Pain Behavior Short Form.

Additional secondary efficacy endpoints include the following:

- Number of days in the hospital (for any reason including, but not limited to, HC) over the 24-week study period.
- Time to resolution of viremia for each target virus (ie, BKV, AdV, CMV, HHV-6, JCV, and/or EBV) over the 24-week study period (only for participants with detectable viremia at randomization). Evaluation of this endpoint will be based on viremia quantitation performed at the central laboratory. Resolution of viremia will be defined by the lower limits of quantitation (LLOQ) of the assays used (BKV, AdV, CMV, HHV-6, JCV are measured in the plasma, EBV is measured in peripheral blood mononuclear cells).
- Average daily bladder pain over the 24-week study period, without use of prescription pain medications (not PRN or "as needed") or supportive bladder care.

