2.3.3 Exploratory Efficacy Endpoints

The exploratory efficacy endpoints include the following:

• Cumulative days and time to discontinuation of supportive bladder care for HC, specifically continuous bladder irrigation and/or nephrostomy tubes.

- Summary of HC-associated signs and symptoms other than bladder pain, including urinary frequency, urinary urgency, constant need to urinate, and nocturia.
- Incidence and time to recurrence of HC, defined as two consecutive Bedi grades ≥2 with macroscopic hematuria (visibly bloody urine) that are at least 2 days apart.
- Incidence and time to recurrence of bladder pain.
- Requiring RBC and/or platelet transfusions and the number of required RBC and/or platelet transfusions (measured in transfusion units/participant).
- Change in renal function as assessed by eGFR. For participants requiring dialysis, number of days on dialysis will be captured.
- Time to resolution of BK viruria. Resolution of viruria will be defined by the lower limits of quantitation of the assay used.
- Viremia and viruria with each target virus (ie, BKV, AdV, CMV, HHV-6, JCV, and/or EBV) over time.
- Length of use of any pain medication(s) (IV, oral, or other), including antispasmodics, anticholinergics, and beta-3-agonists, used for control of lower abdominal/bladder pain.
- Use of immunosuppressive agents, by specific agent during the study.
- Number of hospitalizations, number of ICU stays, and number of days of ICU care for any reason.
- Use of antiviral therapies other than cidofovir with potential activity against at least one target virus by specific agent during the study.
- Overall survival, defined as time to death (from any cause) from the time of randomization in days.
- Incidence of relapse or progression of the primary malignancy.
- Overall quality of life as measured by EQ-5D questionnaires.
- Global impression of hemorrhagic cystitis change.

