3.4.2 Key Secondary Efficacy Endpoint

The key secondary endpoint is the time to resolution of bladder pain as measured by age appropriate COAs. Resolution of pain is defined as participants achieving a score on the relevant COA that does not exceed "mild pain" (defined in Protocol Section 7), confirmed with 2 consecutive scores, without use of prescription pain medications (not PRN or "as needed) or supportive bladder care. The relevant COA is the worst daily pain (ie, the participant's worst bladder pain over the previous 24 hours), which is recorded daily for the first 6 weeks of the study and once weekly thereafter. Intermittent missing scores will be omitted.

The analysis will include all the participants whose pain scores exceed "mild pain" at randomization or who use prescription pain medications (not PRN or "as needed") or supportive bladder care at randomization, assuming their bladder pain scores exceed mild. If the scores at randomization are missing, a prior pain score will be used if available. Otherwise, the participant will not be included in the analysis.

Time to resolution will be calculated from the date of randomization to the date of the first resolution of bladder pain. Participants not observed to achieve resolution will be considered censored at their last follow up. The pain scores collected while participants use pain medications (not PRN or "as needed") or supportive bladder care will not be used.

If the result of the analyses of the primary efficacy endpoint is statistically significant based on both the BK ITT and overall ITT Populations, a formal hypothesis test will be conducted sequentially of the time to resolution of bladder pain based on the BK ITT Population in the same manner as described for the primary efficacy analysis of the primary efficacy endpoint, and a one-sided 0.025 significance level will be used. If this result of the analysis of time to resolution of bladder pain based on the BK ITT Population, a formal hypothesis test of this endpoint will then be conducted based on the overall ITT Population using a 0.025 significance level.

A sensitivity analysis of the key secondary efficacy endpoint will also be conducted for the BK ITT population, using a Cox proportional hazards model in order to account for additional potential confounders of the treatment effect. In addition, supportive analyses of the key secondary efficacy endpoint will also be performed based on the BK mITT, BK PP and mITT Populations.

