Cumulative days of supportive bladder care for HC, specifically continuous bladder irrigation and/or nephrostomy tubes, will be summarized by treatment group. In the analysis, cumulative days of supportive bladder care will include all days of such therapy for the entirety of the trial. Time to discontinuation refers to time from randomization to initial discontinuation of all supportive bladder care in participants who were receiving a supportive bladder care at randomization. Time to discontinuation of supportive bladder care for HC will be analyzed using Kaplan-Meier estimates, and treatment effect will be compared using stratified log-rank test and hazard ratio with stratified Cox proportional model.

HC-associated signs and symptoms other than bladder pain will be descriptively summarized. The signs and symptoms analyzed include urinary frequency, urinary urgency, constant need to urinate, and nocturia.

Incidence and time to recurrence of HC will be analyzed using Kaplan-Meier estimates, and treatment effect will be compared using stratified log-rank test and hazard ratio with stratified Cox proportional model. Only participants who have reached the HC resolution will be included in the analysis. Time to recurrence of HC refers to time from the HC resolution to the time when the initial Bedi grade to evaluate for recurrence demonstrates a Bedi Grade ≥2 with macroscopic hematuria.

Incidence and time to recurrence of bladder pain will be analyzed using the same methods. Only participants who have reached the bladder pain resolution will be included in the analysis. Time to recurrence of bladder pain refers to time from the bladder pain resolution to the time when the initial pain score exceeds "mild pain" without use of prescription pain medications or supportive bladder care.

The number of participants requiring RBC and/or platelet transfusions and the number of required RBC and/or platelet transfusions (measured in transfusion units/participant) will be summarized by treatment group.

Change in renal function as assessed by eGFR and number of days on dialysis for participants requiring dialysis will be summarized by treatment group.

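### Exploratory bladder-pain recurrence is triggered by one unconfirmed score above mild, so diary noise can inflate it, more so in participants who resolve early

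*SAP*

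**What the plan says.** SAP 2.3.3 lists incidence and time to recurrence of bladder pain as an exploratory endpoint without defining it. The only working definition is in SAP 3.4.3: "Time to recurrence of bladder pain refers to time from the bladder pain resolution to the time when the initial pain score exceeds" mild pain. The same sentence counts only scores recorded off prescription pain medication and off supportive bladder care. The analysis covers participants who reached pain resolution and uses Kaplan-Meier estimates, a stratified log-rank test and a stratified Cox hazard ratio, with no multiplicity adjustment.

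Three other passages bear on it:

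- **Pain resolution (SAP 3.4.2)** must be "confirmed with 2 consecutive scores". Mild is "a score ≤3 on the worst daily pain question from the Bladder Pain/Interstitial Cystitis Symptom Diary (BPIC SD") from age 12, and "a score ≤2 on the Wong-Baker FACES® Pain Rating Scale" at ages 3 to 11.
- **HC recurrence (SAP 2.3.3)** is "defined as two consecutive Bedi grades ≥2 with macroscopic hematuria (visibly bloody urine) that are at least 2 days apart".
- **Diary schedule.** SAP 3.4.2 describes worst daily pain as a score "which is recorded daily for the first 6 weeks of the study and once weekly thereafter". Protocol 7.2.1 agrees: "at baseline, then daily through Week 6, followed by weekly to Week 24".

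**The concern.** Resolution and recurrence share one boundary. From age 12, a score of 3 is resolved and a 4 is a recurrence, with no minimum change and no confirmation. One bad day in a participant whose underlying pain has not changed ends the follow-up for this endpoint as an event.

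The schedule adds a second problem. During the daily phase there are seven chances a week of a stray score; afterwards there is one. The false-event rate therefore depends on when a participant resolved. Earlier pain resolution is what the key secondary endpoint hopes to show for posoleucel (PSL). If it happens, the recurrence curve, log-rank test and hazard ratio can make the faster arm look less durable when nothing real differs.

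**Working it through.** The plan states no recurrence rate and no day-to-day variability for pain, so there is no figure of its own to reproduce. The check uses the plan's schedule with an assumed noise rate.

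**Step 1. Scores at risk.** Inputs from SAP 3.4.2 and SAP Appendix A: daily to Day 42, then one score a week in Weeks 7 to 24 (18 scores). Resolution on day d is confirmed on day d+1, so in the daily phase the later scores number n = 42 − (d+1) + 18.

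- Day 7: 42 − 8 + 18 = 52
- Day 14: 42 − 15 + 18 = 45
- Day 28: 42 − 29 + 18 = 31
- Day 41: 42 − 42 + 18 = 18
- Week 12, confirmed Week 13: 24 − 13 = 11

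**Step 2. False recurrence with no true worsening.** Let q be the chance that a single score exceeds mild by noise (assumed), with independent scores and complete diaries. One-score rule: 1 − (1 − q)^n. Two-score rule: exact recursion for at least one run of two.

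| Resolved | n | q=1%: one / two | q=2%: one / two | q=5%: one / two |
|---|---|---|---|---|
| Day 7 | 52 | 40.7% / 0.5% | 65.0% / 2.0% | 93.1% / 11.5% |
| Day 41 | 18 | 16.5% / 0.2% | 30.5% / 0.7% | 60.3% / 4.0% |
| Week 12 | 11 | 10.5% / 0.1% | 19.9% / 0.4% | 43.1% / 2.4% |

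**Step 3. How much noise makes it more than half?** Solve 1 − (1 − q)^n = 0.5, so q = 1 − 0.5^(1/n): 1.3% (Day 7), 1.5% (Day 14), 2.2% (Day 28), 3.8% (Day 41), 6.1% (Week 12).

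**Step 4. What q might be.** For a rounded 0-10 score with a stable normal level, q = 1 − Φ((3.5 − level)/SD). Levels and SDs are assumptions.

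| Level, SD | q | Day 7 | Day 41 |
|---|---|---|---|
| 1, 0.75 | 0.04% | 2% | 1% |
| 1, 1 | 0.62% | 28% | 11% |
| 1.5, 1 | 2.28% | 70% | 34% |
| 2, 1 | 6.68% | 97% | 71% |

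**Step 5. Does Kaplan-Meier censoring remove the gradient?** Only the part due to longer follow-up. Take the first 11 weeks after confirmation. A Day 7 resolver has 34 daily scores (Days 9 to 42) plus 6 weekly ones (Weeks 7 to 12), 40 in all; a Week 12 resolver has 11. At q = 2% that is 1 − 0.98^40 = 55% against 1 − 0.98^11 = 20%. Per week, the false-event chance is 1 − 0.98^7 = 13% in the daily phase and 2% afterwards.

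**Step 6. By arm.** No pain-resolution medians are given. Borrowing the hematuria medians in SAP 2.2.3 (6 weeks PSL, 12 weeks placebo, exponential), with equal noise in both arms, simulated false recurrence is:

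| q | One score: PSL v placebo | Two scores: PSL v placebo |
|---|---|---|
| 1% | 22% v 18% | 0.3% v 0.2% |
| 2% | 38% v 31% | 1.0% v 0.8% |
| 5% | 64% v 55% | 5.8% v 4.6% |

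**Step 7. Correlated scores.** With lag-1 correlation 0.5, level 1 and SD 1.5, a Day 7 resolver goes from 88.2% under one score to 27.8% under two. The gain remains but is smaller than under independence.

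**The case against.** The best counter-argument is that the sentence only dates the event. The neighbouring paragraph in SAP 3.4.3 dates HC recurrence at its initial Bedi grade in parallel words and also names no second reading, so the initial pain score could be the first of a pair. This fails on the text: HC recurrence has a written two-reading rule in SAP 2.3.1 and 2.3.3, and pain has none anywhere. Someone programming from the plan would use one score.

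Other points stand, and limit what can be claimed:

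- A reader might infer that most resolved participants will falsely recur, or that the endpoint mostly counts noise. The documents do not support this. It depends on a noise rate they do not give, and resolved participants are off scheduled prescription analgesia and bladder care, so low levels such as those in the first two rows of Step 4 are plausible. Calling it mostly noise would also need a true recurrence rate.
- A reader might infer that pain recurrence is the SAP's only unconfirmed endpoint. It is not: resolution of viremia and of BK viruria also state no confirmation.
- A reader might infer that PSL must look worse. That needs earlier pain resolution on PSL and similar noise in both arms. If PSL also lowers residual pain, the gap could vanish or reverse.
- Missed diaries, dropout and the exclusion of scores on medication all reduce the number of countable scores below those in Step 1.
- Confirmation alone could lose real events. A participant with one high score who restarts scheduled analgesia before the next diary has no second countable score under the present sentence.

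**Conclusion.** The point holds in a limited form. As written, one score above mild counts as recurrence, against the two-reading standard the SAP applies to pain resolution and HC recurrence. The excess of false recurrences in early resolvers follows from the daily-then-weekly schedule at any equal, non-zero noise rate. Its size does not follow from the documents: the 65%, 30% and 20% figures assume 2% noise per score, independent scores and complete diaries, and the range in Step 4 runs from about 1% to 97%. A sizeable share of resolved participants can be affected; a majority is possible but not established. Any arm-level bias would run against the arm that resolves pain sooner, by 4 to 9 percentage points under the borrowed medians and equal noise in Step 6.

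The endpoint is exploratory, unadjusted and outside the testing hierarchy, so the consequence is confined to how durability of pain relief is read.

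**What to change.** In SAP 3.4.3, define bladder-pain recurrence as two consecutive assessments above mild after confirmed resolution, dated at the first. State that use of scheduled (not PRN) prescription pain medication or supportive bladder care counts as above mild. This matches SAP 2.3.2 and the SAP 3.4.2 estimand table, and restores the not-PRN qualifier that the present sentence omits. Put the same definition in SAP 2.3.3.

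Add a sensitivity analysis on a common weekly grid, because confirmation shrinks the daily/weekly gradient but does not remove it (2.0% against 0.4% at q = 2% in Step 2).

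Cost: a few sentences and some programming, with no new data. Downsides: a recurrence first seen on the last diary stays unconfirmed, flares shorter than a week after Week 6 are not counted, and the noise reduction is smaller if daily scores are correlated.

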2.3 Study Endpoints

2.3.1 Primary Efficacy Endpoint

The primary endpoint is the time to resolution of macroscopic hematuria in participants with documented BK viruria. A supplementary analysis will evaluate the time to resolution of macroscopic hematuria in participants with any virus-associated HC. Resolution of macroscopic hematuria is defined as resolution to Grade 0 or 1 on the Bedi scale as assessed by the Investigator on 2 consecutive visual urine assessments with urinalysis ≥2 days apart without continuous bladder irrigation or nephrostomy tubes that are uncapped. However, if a participant has nephrostomy tubes that are capped, Bedi assessments may be performed on urine voided through the urethra or a bladder catheter (eg, Foley or suprapubic catheter), including for the purpose of assessing for resolution.

A healthcare provider (HCP) on the study team (including a home health provider) may perform the visual urine assessment, but it is the Investigator's responsibility to determine the Bedi grade. Grade 0 requires no detectable blood by urinalysis; Grade 1 hematuria requires confirmation of resolution by urinalysis results of ≤100 RBCs/high power field (HPF).

Participants will be followed for the primary endpoint for a maximum of 24 weeks from the date of randomization.

Definitive therapies to stop bladder bleeding, including cystectomy, bladder vessel embolization, cauterization, fulguration, or formalin instillation are permitted, but will be considered treatment failures for the primary endpoint of time to resolution of macroscopic hematuria. Participants with ongoing continuous bladder irrigation should be evaluated daily by the Investigator for the ability to discontinue this supportive measure.

Participants who are receiving continuous bladder irrigation or who have nephrostomy tubes that are uncapped at randomization will be considered to have Bedi Grade 3 hematuria at randomization. For participants undergoing continuous bladder irrigation, the primary endpoint (ie, time to resolution of macroscopic hematuria) will be measured once participants discontinue continuous bladder irrigation. Bedi grading will not be performed on days on which the participant is receiving continuous bladder irrigation. Discontinuation of continuous bladder irrigation will be based upon the participant's clinical condition and the treating physician's medical judgement.

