If, following resolution of macroscopic hematuria, recurrence is observed, a Bedi assessment with urinalysis will be obtained and the date of recurrence observed by the Investigator will be recorded. Urine obtained at the time of recurrence will also be sent for BKV, AdV, CMV, HHV-6, JCV, and EBV viral load determination and banking of viral deoxyribonucleic acid for potential genotyping. A second Bedi assessment with urinalysis will be repeated ≥2 days after the date of recurrence observed by the Investigator. Recurrence is defined as 2 consecutive Bedi grades ≥2 with macroscopic hematuria (visibly bloody urine) that are at least 2 days apart. Participants with recurrence will then undergo visual assessment of urine and urinalysis as indicated in Table 1 for those with unresolved hematuria and according to the participant's treatment location and time on study. Following resolution of recurrent hematuria, follow Table 1 for those with resolved hematuria.

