Secondary efficacy endpoint in the estimand framework is described as follows:

Statistical category	 Estimand: Treatment: Study Treatment (PSL) or Placebo Population: Pediatric and adult participants with virus-associated hemorrhagic cystitis following allogeneic HCT Endpoint (Variable): Time to resolution of bladder pain as measured by age appropriate COAs. Resolution of pain is defined as participants achieving a score on the relevant COA that does not exceed "mild pain" (defined in Protocol Section 7), confirmed with 2 consecutive scores, without use of prescription pain medications (not PRN or "as needed") or supportive bladder care. Intercurrent events: Include intercurrent events from primary efficacy endpoint and 1. Use of prescription pain medications (not PRN or "as needed") or supportive bladder care 2. Early discontinuation from the study treatment before achieving resolution 3. Death due to any cause before achieving resolution 4. Missing daily or weekly assessment of bladder pain 5. Treatment for hemorrhagic cystitis with non-PSL VSTs before achieving resolution 		
	resolution Analysis set Intercurrent event handling Population-le		
	-	strategy	summary (Analysis):
Secondary	BK ITT	 Composite strategy: Data collected while on ICE 1 will not be used for the key secondary endpoint, ie, assuming using ICE 1 is equivalent to pain exceeds "mild pain." Treatment policy strategy: Data collected after occurrence of ICE 2 will be used for the key secondary endpoint. Composite strategy: Participants with ICE 3 will be censored at the last follow-up time of any participant. Hypothetical strategy: ICE 4 will be omitted and next observed assessment will be used Composite strategy: Participants with ICE 5 will be considered treatment failures for the key secondary endpoint of time to resolution of bladder pain and will be censored at the last follow-up time of any participant. 	As primary but using a one-sided 0.025 significance level.
Supportive 1	BK mITT	Same as secondary	Same as secondary
Supportive 2	mITT	Same as secondary	Same as secondary

Subgroup analyses may be conducted for the BK ITT population for age appropriate COAs to evaluate responses in participants who took different outcome measurements, similar to the primary efficacy endpoint.

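### SAP 3.4.3 dates bladder-pain recurrence only from an off-treatment score, reversing the SAP's rule for resolution, so recurrences that are retreated first can be missed or dated late

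*SAP*

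**What the plan says.** **Pain recurrence.** SAP 3.4.3 (Other Efficacy Endpoints) analyses participants whose bladder pain has resolved. It runs the clock from resolution to the time when the "initial pain score exceeds 'mild pain' without use of prescription pain medications or supportive bladder care". A single score suffices. Nothing makes restarting treatment an event, and the sentence has no exemption for PRN use.

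**Pain resolution.** SAP 2.3.2 treats the same therapies the opposite way: "Use of prescription pain medications (not PRN or 'as needed') or supportive bladder care will be considered equivalent to pain that exceeds 'mild pain". The estimand table in SAP 3.4.2 handles them as a composite, "assuming using ICE 1 is equivalent to pain exceeds 'mild pain", and the text of 3.4.2 adds: "The pain scores collected while participants use pain medications (not PRN or 'as needed') or supportive bladder care will not be used".

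**HC recurrence.** SAP 2.3.1 states: "Recurrence is defined as 2 consecutive Bedi grades ≥2 with macroscopic hematuria (visibly bloody urine) that are at least 2 days apart". SAP 3.4.3 dates the event at the first of the two grades. SAP 2.3.1 also says: "Bedi grading will not be performed on days on which the participant is receiving continuous bladder irrigation". SAP 3.4.1 regards a non-evaluable Bedi assessment as unresolved hematuria if the participant is on irrigation, has uncapped nephrostomy tubes or has visibly bloody urine. That rule stands in the primary endpoint section and is not extended to recurrence.

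Both recurrence endpoints receive Kaplan-Meier estimates, a stratified log-rank test and a hazard ratio (SAP 3.4.3).

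**The concern.** Being off prescription analgesia and supportive care is a sensible condition for a good outcome: resolution should not be credited while treatment masks the pain. Attached to a bad outcome, the same condition works backwards, because the retreatment that signals a relapse removes the score that would have recorded it.

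The primary endpoint is dated at first resolution, and no rule reverses it on relapse. The recurrence endpoints are therefore where the plan looks at durability. If recurrences can drop out because they were treated, the incidence and Kaplan-Meier curves look more favourable than the clinical course. The comparison between arms is then open to distortion from any difference in how promptly participants are retreated.

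**Working it through.** The documents give no recurrence rate or retreatment rate, so there is no plan figure to reproduce. The check is a comparison of the rules, followed by an illustration on assumed inputs.

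**Step 1. Pain: the two rules applied to the same post-resolution course**

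| Course after resolution | Rule in SAP 2.3.2 and 3.4.2 | Recurrence rule in SAP 3.4.3 |
|---|---|---|
| High score, no treatment | Above mild | Event |
| High score, then scheduled analgesia | Above mild | Event, dated at the score |
| Scheduled analgesia or supportive care before any high score is entered | Equivalent to above mild | No event |
| High score during PRN prescription use | Score is used; above mild | No event |

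The last two rows conflict. Resolution can be reached on PRN medication but not on scheduled medication or supportive care. Scheduled use after resolution is therefore always a new start, whereas PRN use may simply continue and block every later score.

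**Step 2. HC: what irrigation does to the two-grade rule**

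| Course after resolution | Result |
|---|---|
| Bloody grade, irrigation, bloody grade afterwards | Can count, dated at the first grade: SAP 2.3.1 sets no upper limit on the interval |
| Bloody grade, irrigation, urine clear at the next grade | Not counted |
| Irrigation before any grade | Not counted unless two bloody grades follow, and then dated late |
| Transfusion, hydration or intravesical agent without irrigation | Grading continues; counts if two bloody grades are recorded |

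The gap is the second and third rows.

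**Step 3. Effect on incidence (illustration)**

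Let p be true recurrence and m the share retreated before a qualifying score or grade and never captured later. Observed incidence = p × (1 − m). Assume p = 30%:

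- m = 25%: 0.30 × 0.75 = 22.5%
- m = 50%: 0.30 × 0.50 = 15%
- m = 75%: 0.30 × 0.25 = 7.5%

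With the same m in both arms, the ratio of incidences is undistorted. With equal true recurrence but m of 25% against 50%, the arms show 22.5% against 15%, a spurious ratio of 0.75 / 0.50 = 1.5. With 25% against 75% the ratio is 0.75 / 0.25 = 3.0. These ratios do not depend on p. Lost or delayed events also lengthen Kaplan-Meier time to recurrence.

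**Step 4. Where in follow-up the pain loss falls**

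Scores are daily through Week 6 and weekly afterwards (Protocol 7.2.1 and 7.2.2; SAP 3.4.2). Suppose treatment starts within 2 days of onset. A completed daily diary then misses almost nothing. A weekly entry falls outside those 2 days with probability 5/7. If 40%, 60% or 80% of recurrences after Week 6 are treated that quickly, the share missed at onset is 0.4 × 5/7 = 29%, 0.6 × 5/7 = 43% or 0.8 × 5/7 = 57%. The 2-day window and the treated shares are assumptions.

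**The case against.** The strongest reply is that the consequence is small. Both endpoints are exploratory, outside the testing hierarchy and without multiplicity adjustment, so no confirmatory test is touched. Retreatment is also visible elsewhere: SAP 3.4.3 reports cumulative supportive-care days and total days on pain medication. The first part stands. The second stands only in part, because those are whole-trial totals that do not identify a relapse after resolution.

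A reader might go further than the text allows in four ways.

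- **That severe or treated recurrences are always missed.** One score above mild entered before treatment begins counts at once, however severe, and some cases could still register after treatment stops. Such recurrences can be missed; the text does not show that they all are.
- **That irrigation prevents HC recurrence from being counted.** It bars grading only on irrigation days. The protocol repeats the assessment at 48 to 72 hours (7.1.9), but the SAP asks only for 2 days or more, so grades on either side of irrigation can pair. SAP 2.3.1 also assigns Grade 3 to irrigation or uncapped tubes at randomization, and SAP 3.4.1 calls such assessments unresolved. Neither is stated for recurrence, so this part is a gap in scope rather than a reversed rule.
- **That 29% to 57% of all recurrences are lost.** Those figures rest on assumed rates and apply only to the weekly diary.
- **That one arm is favoured.** Nothing in the documents shows that retreatment before capture would differ by arm.

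**Conclusion.** The point holds for pain as a contradiction within the SAP. The same treatments mean pain above mild for resolution and no event for recurrence, and the PRN exemption is present in one rule and absent from the other. That conclusion needs no assumed rate. For HC it holds in the narrower form: participants irrigated before any grade, or whose urine clears before the second grade, can go uncounted.

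The direction is lower incidence and longer time to recurrence. The size is unknown, and the percentages above are illustrations on assumed inputs. Bias between arms requires a difference in retreatment before capture. The primary and key secondary tests are unaffected. The matter still merits correction before analysis, because a stated event rule feeds a reported log-rank test and hazard ratio on durability.

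**What to change.** Change the analysis definitions in SAP 3.4.3 (and the matching HC definition in 2.3.1 and 2.3.3); no clinical procedure changes.

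- **Pain recurrence:** the first date after resolution of either (a) a score above mild pain, regardless of treatment, or (b) the start of prescription medication for bladder pain, other than PRN, or of supportive bladder care. This matches SAP 2.3.2 and 3.4.2, including the PRN wording.
- **HC recurrence:** keep the two-grade rule and add one visibly bloody grade of 2 or more followed, before a second grade, by continuous bladder irrigation, an uncapped nephrostomy tube or a definitive therapy. Date it at that first bloody grade.
- **Non-evaluable assessments:** state that the unresolved rule in SAP 3.4.1 also applies to recurrence, and give the date to be used. This covers participants irrigated before any grade.

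The cost is SAP text and derivation code. Pain scores, the pain medication log (Protocol 7.2.4), medication dates (6.6.3), supportive care (6.6.2) and Bedi assessments are already collected. After Week 6 the log is weekly, so start dates should be taken from the concomitant medication record where the two differ in precision.
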